### **6.4 Observational Period (Cycle X + 2)**

If Chemotherapy Day in Cycle X+2 is delayed, record the reason for delay in the eCRF. If the delay is due to laboratory results, record the relevant results in the eCRF.

#### **6.4.1 Chemotherapy Day in Cycle X + 2 (Visit 9)**

The following procedures will be performed on Cycle X + 2, Day 1 at Visit 9 prior to chemotherapy dosing:

- Perform ISTH bleeding assessment (see [Appendix D](#));
- Record concomitant medications;
- Assess functional status using the ECOG Performance Status Scale;

- Assess adverse events;
- Collect blood samples for the following assessments prior to chemotherapy dosing:
  - Hematology (including platelet counts);
  - Coagulation; and
  - Serum chemistry;
- Assess chemotherapy dose modifications/schedule; and
- Assess whether subject required platelet transfusion.

#### **6.4.2 Cycle X + 2 Days 11 ( $\pm 1$ day), 15 ( $\pm 1$ day), and 18 ( $\pm 1$ day) (Visits 10, 11, and 12)**

The following procedures will be performed on Cycle X + 2, Days 11, 15, and 18 at Visits 10, 11, and 12:

- Record concomitant medications;
- Assess adverse events;
- Collect blood samples for the following assessments:
  - Platelet counts;
- Assess chemotherapy dose modifications/schedule; and
- Assess whether subject required platelet transfusion.

#### **6.4.3 Follow-Up Visit (For subjects not continuing into the optional Open-Label Extension Period)**

##### **6.4.3.1 Prior to Chemotherapy Day in Cycle X + 3 (Visit 17)**

For subjects not continuing into the optional OLE Period, a Follow-Up Visit will occur prior to (within 3 days) Chemotherapy Day in Cycle X + 3. If Cycle X + 2 is the subject's last chemotherapy cycle, a Follow-Up Visit will occur at 30 days ( $\pm 3$  days) after Chemotherapy Day in Cycle X + 2. Subjects will complete Visit 17 procedures in [Section 6.5.5](#).

#### **6.5 Optional Open-Label Extension Period (Cycle X + 3 and On)**

##### **6.5.1 Pre-Chemotherapy Avatrombopag Treatment (Visit 13)**

Subjects will receive avatrombopag once daily for 5 days prior to Chemotherapy Day in Cycle X + 3 (Visit 13). For Cycle X + 4, this visit will be denoted Visit 13.1 and for Cycle X + 5, this visit will be denoted Visit 13.2. This numbering scheme will continue for subsequent enrolled open-label cycles.

The following procedures will be performed on the first day of pre-chemotherapy avatrombopag treatment at Visit 13 prior to avatrombopag dosing:

- Conduct eligibility assessment based on OLE inclusion/exclusion criteria;
- Assess functional status using the ECOG Performance Status Scale;

- Contact IRT;
- Perform ISTH bleeding assessment (see [Appendix D](#));
- Record concomitant medications;
- Assess adverse events;
- Record vital signs (includes blood pressure and pulse rate);
- Collect blood samples for the following assessments prior to IP dosing:
  - Hematology (including platelet counts);
  - Coagulation; and
  - Serum chemistry;
- Perform pregnancy test (urine or serum) for female subjects of childbearing potential only;
- Assess chemotherapy dose modifications/schedule;
- Assess whether subject required platelet transfusion;
- Dispense avatrombopag;
- Administer or self-dose avatrombopag with food.

#### **6.5.2 Chemotherapy Day (Visit 14, Cycle X + 3 Day 1 to 3)**

For Cycle X + 4, this visit will be denoted Visit 14.1 and for Cycle X + 5, this visit will be denoted Visit 14.2. This numbering scheme will continue for subsequent enrolled open-label cycles.

The following procedures will be performed on Cycle X + 3, Day 1 at Visit 14 prior to chemotherapy dosing:

- Perform ISTH bleeding assessment (see [Appendix D](#));
- Record concomitant medications;
- Assess adverse events;
- Perform symptom-directed physical examination;
- Record vital signs (includes blood pressure and pulse rate);
- Collect blood samples for the following assessments:
  - Hematology (including platelet counts)
- Assess chemotherapy dose modifications/schedule;
- Assess whether subject required platelet transfusion; and
- Collect unused avatrombopag, if applicable.

The following procedures will be performed on post-chemotherapy dosing (these procedures will be performed on the last Chemotherapy Day of the cycle):

- Dispense avatrombopag

### **6.5.3 Post-Chemotherapy Avatrombopag Treatment (Visit 15)**

For Cycle X + 4, this visit will be denoted Visit 15.1 and for Cycle X + 5, this visit will be denoted Visit 15.2. This numbering scheme will continue for subsequent enrolled open-label cycles.

The following procedures will be performed on the last day of the 5-day post-chemotherapy avatrombopag treatment at Visit 15:

- Contact IRT;
- Perform ISTH bleeding assessment (see [Appendix D](#));
- Record concomitant medications;
- Assess adverse events;
- Collect blood samples for the following assessments:
  - Hematology (including platelet counts);
  - Coagulation; and
  - Serum chemistry;
- Assess chemotherapy dose modifications/schedule;
- Assess whether subject required platelet transfusion;
- Administer or self-dose avatrombopag with food; and
- Collect unused avatrombopag, if applicable.

### **6.5.4 Cycle X + 3 Day 15 (±1 day) (Visit 16)**

For Cycle X + 4, this visit will be denoted Visit 16.1 and for Cycle X + 5, this visit will be denoted Visit 16.2. This numbering scheme will continue for subsequent enrolled open-label cycles. The following procedures will be performed on Cycle X + 3, Day 15 at Visit 16:

- Record concomitant medications;
- Assess adverse events;
- Perform ISTH bleeding assessment (see [Appendix D](#));
- Collect blood samples for platelet counts;
- Assess chemotherapy dose modifications/schedule; and
- Assess whether subject required platelet transfusion.

### **6.5.5 Follow-Up Visit**

#### **6.5.5.1 Thirty days after last avatrombopag dose (Visit 17) in the OLE Period**

The following procedures will be performed 30 days (±3 days) after last avatrombopag dose at Visit 17:

- Contact IRT;
- Perform ISTH bleeding assessment (see [Appendix D](#));

- Assess functional status using the ECOG Performance Status Scale;
- Record concomitant medications;
- Assess adverse events;
- Perform full physical examination;
- Record vital signs (includes blood pressure and pulse rate);
- Collect blood samples for the following assessments:
  - Hematology (including platelet counts);
  - Coagulation; and
  - Serum chemistry;
- Perform pregnancy test (urine) for female subjects of childbearing potential only; and
- Assess whether subject required platelet transfusion.

#### **6.6 Early Termination Visit and Withdrawal Procedures**

For subjects who are withdrawn from the study prior to the Follow-Up Visit, all Visit 13 (for subjects not continuing into the optional OLE Period) or Visit 17 (for subjects continuing into the optional OLE Period) procedures will be performed at an Early Termination Visit. These procedures include the following:

- Contact IRT;
- Perform ISTH bleeding assessment (see [Appendix D](#));
- Assess functional status using the ECOG Performance Status Scale;
- Record concomitant medications;
- Assess adverse events;
- Perform full physical examination;
- Record vital signs (includes blood pressure and pulse rate);
- Collect blood samples for the following assessments:
  - Hematology (including platelet counts);
  - Coagulation; and
  - Serum chemistry;
- Perform pregnancy test (urine) for female subjects of childbearing potential only;
- Assess whether subject required platelet transfusion; and
- Collect unused IP, if applicable.

## **6.7 Long-Term Follow-Up**

After the Follow-Up Visit, all subjects will be contacted approximately every 6 months for up to 5 years by telephone during the Long-Term Follow-Up Period for documentation of vital status (if death occurred, record of date of death) and occurrence of secondary malignancies. If a secondary malignancy has occurred, the following information will be collected: date of onset and type of malignancy, as well as a written narrative from the clinical site summarizing the course of events leading up to diagnosis of the secondary malignancy.

## 7 EFFICACY ASSESSMENTS

The primary efficacy endpoint is the proportion of responders who meet all of the following criteria during the period after post-chemotherapy IP treatment in Cycle X+1 through Chemotherapy Day of Cycle X+2:

- Not requiring a platelet transfusion;
- Not requiring a chemotherapy dose reduction by  $\geq 15\%$  due to thrombocytopenia; and
- Not requiring a chemotherapy delay by  $\geq 4$  days due to thrombocytopenia.

The key secondary efficacy endpoints include the following:

- Duration of severe thrombocytopenia defined as a platelet count  $< 50 \times 10^9/L$  during the period after post-chemotherapy IP treatment in Cycle X+1 through Chemotherapy Day of Cycle X+2;
- Change in platelet count from baseline (qualifying chemotherapy cycle [Cycle X]) (nadir) to Cycle X + 1 (nadir);
- Proportion of subjects who do not have major or non-major clinically relevant bleeding during the period after post-chemotherapy IP treatment in Cycle X+1 through Chemotherapy Day of Cycle X+2; and
- Proportion of subjects who do not receive a platelet transfusion during the period after post-chemotherapy IP treatment in Cycle X+1 through Chemotherapy Day of Cycle X+2.

The other efficacy endpoints include the following during the period after post-chemotherapy IP treatment in Cycle X+1 through Chemotherapy Day of Cycle X+2:

- Proportion of subjects who do not have a chemotherapy dose reduction that is  $\geq 15\%$  due to thrombocytopenia;
- Proportion of subjects who do not have a chemotherapy delay that is  $\geq 4$  days due to thrombocytopenia;
- Proportion of subjects with a pre-defined post-baseline nadir platelet count; and
- Proportion of subjects achieving a pre-defined post-baseline maximum platelet count

Blood samples to assess platelet count will be collected as indicated in [Appendix A](#). Local laboratories may be used to determine study eligibility; however, for study analysis and reporting purposes, only values determined at a central laboratory will be used with the exception of platelet count. Local laboratories may be used if immediate results are clinically needed.

Whether a subject requires a platelet transfusion will be determined by the Investigator or treating physician.

Bleeding will be evaluated by the Investigator using the non-surgical ISTH bleeding definitions described in [Appendix D](#).

## **8 PHARMACOKINETIC AND PHARMACODYNAMIC ASSESSMENTS**

### **8.1 Pharmacokinetic Assessments**

Blood samples for PK analysis will be collected as indicated in [Appendix A](#). Additional time points may be collected as necessary.

Pharmacokinetic sampling will occur twice during the study with 4 samples collected on each day.

### **8.2 Pharmacodynamic Assessments**

Blood samples for PD analysis will be collected as indicated in Appendix A.

Pharmacodynamic samples (ie, platelet counts) will be collected throughout each cycle of the study including Cycle X + 1, Cycle X + 2, and each enrolled open-label cycle.

## **9 SAFETY ASSESSMENTS**

### **9.1 Adverse Events**

An adverse event is defined as any untoward medical occurrence in a subject administered a pharmaceutical product, which does not necessarily have a causal relationship with this treatment. An adverse event can therefore be any unfavorable and/or unintended sign (including an abnormal laboratory finding), symptom, or disease temporally associated with the use of an investigational medicinal product, whether or not related to the investigational medicinal product. All adverse events, including observed or volunteered problems, complaints, or symptoms, are to be recorded on the appropriate eCRF.

Adverse events, which include clinical laboratory test variables, will be monitored and documented from the time of informed consent until the Follow-Up Visit occurring prior to (within 3 days) Chemotherapy Day in Cycle X + 3 (for subjects not continuing into the optional OLE Period) and the Follow-Up Visit occurring 30 days after last dose of IP (for subjects continuing into the optional OLE Period). Subjects should be instructed to report any adverse event that they experience to the Investigator. Beginning with the Screening Visit, Investigators should make an assessment for adverse events at each visit and record the event on the appropriate adverse event eCRF. Events associated with disease progression should not be reported as adverse events/SAEs. However, if in the Investigator's opinion the disease progression is manifesting in an unusual or uncharacteristic manner, the associated events should be reported as adverse events/SAEs, as appropriate.

Wherever possible, a specific disease or syndrome (ie, diagnosis) rather than individual associated signs and symptoms should be identified by the Investigator and recorded on the eCRF. However, if an observed or reported sign or symptom is not considered a component of a specific disease or syndrome by the Investigator, it should be recorded as a separate adverse event on the eCRF. Additionally, the condition that led to a medical or surgical procedure (eg, surgery, endoscopy, tooth extraction, or transfusion) should be recorded as an adverse event, not the procedure.

Any medical condition already present at the Screening Visit should not be reported as an adverse event unless the medical condition or signs or symptoms present at baseline changes in severity, frequency, or seriousness at any time during the study. In this case, it should be reported as an adverse event.

Clinically significant abnormal laboratory or other examination findings that are detected during the study or are present at the Screening Visit and significantly worsen during the study should be reported as adverse events. The Investigator will exercise his or her medical and scientific judgment in deciding whether an abnormal laboratory finding or other abnormal assessment is clinically significant. Clinically significant abnormal laboratory values occurring during the clinical study will be followed until repeat tests return to normal, stabilize, or are no longer clinically significant. Laboratory abnormalities are not considered adverse events unless they are associated with clinical signs or symptoms, or require medical intervention. Any abnormal test that is determined to be an error does not require reporting as an adverse event.

Clinically significant abnormal findings in physical examinations will be reported as adverse events.

### 9.1.1 Assessment of Adverse Events by the Investigator

The Investigator will assess the severity (intensity) of each adverse event and will also categorize each adverse event as to its potential relationship to IP using the categories of yes or no.

#### Assessment of Severity:

The severity of all adverse events should be graded according to the Common Terminology Criteria for Adverse Events (CTCAE). For those adverse events not listed in the CTCAE, the following grading system should be used:

- Mild (CTCAE Grade 1): Transient symptoms, awareness of sign/symptom, but easily tolerated and no interference with subject's daily activities.
- Moderate (CTCAE Grade 2): Marked signs/symptoms that interfere with subject's usual activities, but still acceptable.
- Severe (CTCAE Grade 3): Incapacitating signs/symptoms which cause considerable interference with the subject's daily activities, unacceptable.
- Life-threatening (CTCAE Grade 4): Life-threatening or disabling adverse event.
- Death (CTCAE Grade 5): Death-related adverse event.

#### Causality Assessment:

The relationship of an adverse event to the administration of the IP is to be assessed according to the following definitions:

- No (unrelated, not related, no relation) – The time course between the administration of IP and the occurrence or worsening of the adverse event rules out a causal relationship and another cause (concomitant drugs, therapies, complications, etc.) is suspected.
- Yes (related) – The time course between the administration of IP and the occurrence or worsening of the adverse event is consistent with a causal relationship and no other cause (concomitant drugs, therapies, complications, etc.) can be identified.

The definition implies a reasonable possibility of a causal relationship between the event and the IP. This means that there are facts (evidence) or arguments to suggest a causal relationship.

The following factors should also be considered:

- The temporal sequence from IP administration-
  - The event should occur after the IP is given. The length of time from IP exposure to event should be evaluated in the clinical context of the event.
- Underlying, concomitant, intercurrent diseases-
  - Each report should be evaluated in the context of the natural history and course of the disease being treated and any other disease the subject may have.
- Concomitant drug-
  - The other drugs the subject is taking or the treatment the subject receives should be examined to determine whether any of them might be recognized to cause the event in question.

- Known response pattern for this class of IP-
  - Clinical and/or preclinical data may indicate whether a particular response is likely to be a class effect.
- Exposure to physical and/or mental stresses-
  - The exposure to stress might induce adverse changes in the recipient and provide a logical and better explanation for the event.
- The pharmacology and PK of the IP-
  - The known pharmacologic properties (absorption, distribution, metabolism, and excretion) of the IP should be considered.

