## 4 SELECTION AND WITHDRAWAL OF SUBJECTS

### 4.1 Inclusion Criteria for All Subjects

Subjects who meet all of the following criteria will be eligible to participate in the study:

1. Subject is  $\geq 18$  years of age at the time of informed consent;
2. Subject with a diagnosis with ovarian cancer, lung cancer (small cell or non-small cell), or bladder cancer, requiring systemic chemotherapy;
3. Subject is currently receiving a chemotherapy regimen given in a 21-day or 28-day cycle (other chemotherapy cycle lengths are not allowed), including 1 or more of the following agents or class of agents:
  - o Nucleoside analog, including gemcitabine and fluorouracil;
  - o Carboplatin or cisplatin;
  - o Anthracycline; or
  - o Alkylating agent;
4. Subject experienced severe thrombocytopenia, defined as 2 platelet counts  $< 50 \times 10^9/L$  measured at least 24 hours apart, during the qualifying chemotherapy cycle (Cycle X), of their current chemotherapy regimen. Platelet counts obtained per standard of care during Cycle X prior to consent may be used;
5. Subject is planned to receive the same chemotherapy regimen and the same dose(s) on Chemotherapy Day (Days 1-3) of Cycle X+1 as was given in the qualifying chemotherapy Cycle X;
6. Subject has an Eastern Cooperative Oncology Group (ECOG) performance status  $\leq 2$ ;
7. Subject has a life expectancy  $> 12$  weeks at Screening and is able to receive at least 2 additional cycles of the current chemotherapy regimen;
8. Females of childbearing potential must agree to use a highly effective method of contraception (eg, total abstinence; an intrauterine device; hormonal contraceptive given orally, by injection, or by implant; double barrier contraception (i.e., condom + diaphragm); or has a vasectomized partner with confirmed azoospermia) throughout the entire study period and for 30 days after investigational product (IP) discontinuation. If currently abstinent, the subject must agree to use an effective method as described above if she becomes sexually active during the study period or for 30 days after IP discontinuation.

Male subjects must be either surgically sterile or agree to use a double barrier contraception method (combination of male condom with either cap, diaphragm, or sponge with a spermicide) throughout the entire study period and for 30 days after IP discontinuation;

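### The two causality definitions in Protocol 9.1.1 give no category to an event with compatible timing and another identifiable cause, and they conflict with the reasonable-possibility sentence that follows

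*Protocol*

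**What the plan says.** Protocol 9.1.1 asks the investigator to judge the relationship of every adverse event to IP "using the categories of yes or no". There is no intermediate category. Under Causality Assessment, each answer has its own definition:

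- **No**: the time course "rules out a causal relationship and another cause (concomitant drugs, therapies, complications, etc.) is suspected".
- **Yes**: the time course fits a causal link to IP and "no other cause (concomitant drugs, therapies, complications, etc.) can be identified".

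Two further sentences follow: "The definition implies a reasonable possibility of a causal relationship between the event and the IP", and "This means that there are facts (evidence) or arguments to suggest a causal relationship". A list of factors to weigh comes next, including underlying disease, class pattern and the pharmacology of IP. On concomitant drugs it says: "The other drugs the subject is taking or the treatment the subject receives should be examined".

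SAP 9.2 carries the investigator's answer forward as Related or Not Related and adds no definition of its own.

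**The concern.** Each definition joins two conditions with *and*, so the two are not complements. An investigator who finds the timing compatible with IP, and who can also name another cause, has no definition to apply but must still tick a box.

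That situation should be ordinary in this trial. Protocol 4.1 admits only subjects with ovarian, lung or bladder cancer, and requires of each: "Subject is currently receiving a chemotherapy regimen given in a 21-day or 28-day cycle". IP is taken for 5 days before and 5 days after Chemotherapy Day, so an event whose timing fits IP will often fit chemotherapy as well.

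The answer is used in four places:

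- **SAP 9.2**: the overview count, the table by system organ class and preferred term, and the listing of related events.
- **Protocol 9.1.3**: efficacy-endpoint events such as thrombocytopenia are reported as adverse events only if the investigator thinks IP caused them.
- **Protocol 9.4**: after the 30-day follow-up period, the duty to report serious events covers those considered related.
- **Protocol 9.6**: suspected unexpected serious adverse reactions, where suspicion of the drug is the entry condition.

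In the second and third of these, a No can mean that the event is not reported at all.

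**Working it through.** The plan states no figure on this point, so the check is one of logic.

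**Step 1. Cross the two conditions.** Treat timing as either consistent with IP or ruled out, and another cause as either present or absent. This simplifies in the plan's favour: it ignores timing that is merely unclear, and it treats a suspected cause (the term in No) and an identified cause (the term in Yes) as the same.

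| Timing | Other cause | Meets Yes? | Meets No? | Category |
|---|---|---|---|---|
| Consistent | Absent | Yes | No | Related |
| Consistent | Present | No | No | None |
| Ruled out | Present | No | Yes | Not related |
| Ruled out | Absent | No | No | None |

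Two of the 4 combinations have no category. The last row does little harm, because an investigator who has ruled out the timing will naturally answer No. The second row is the real gap.

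**Step 2. See whether the following sentences close the gap.** The reasonable-possibility sentence describes what the definition implies. It does not delete the condition that no other cause can be identified, and a reasonable possibility can exist when another cause is also present. So the same subsection holds two standards:

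- Under the Yes bullet, another identified cause defeats relatedness.
- Under the next two sentences, facts or arguments pointing to IP are enough.

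Nothing says which prevails. The listed factors do not settle it. Looking at concomitant drugs and underlying disease turns up the findings that defeat Yes under the bullet, while class pattern and pharmacology may point the other way.

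**Step 3. Ask which way a forced answer goes.** Take a second-row event. An investigator who holds to the Yes bullet answers No, because another cause is identified. One who holds to the No bullet answers Yes, because timing does not rule IP out. One who follows the reasonable-possibility sentence may also answer Yes. The text alone therefore predicts inconsistency, with under-counting under the first of these readings.

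**Step 4. Size.** Let q be the share of timing-compatible events that have another identified cause. Then 1 − q meet Yes, none meet No, and q meet neither. The documents give no value for q. It could be a minority of events or nearly all of them, depending on how readily investigators accept cancer or chemotherapy as an identified cause. Universal chemotherapy exposure supports the word common, and no number beyond that.

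**The case against.** A reader might infer three stronger things, and the documents support none of them.

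- **That almost no event could be classed as related.** The protocol requires that no other cause can be *identified*, not that none exists. The reasonable-possibility sentence lets an investigator answer Yes, and some events will have no obvious chemotherapy explanation.
- **That a numerical ceiling applies.** Assuming that 80–100% of thromboembolic events have another recorded cause gives 100 − 100 = 0% to 100 − 80 = 20% eligible for Yes. This only restates the assumption.
- **That the safety conclusion is biased towards no harm.** The gap event fails No as surely as it fails Yes, so the direction is not fixed. Investigators are blinded (Protocol 5.3), so the same rule meets both arms.

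The main safety comparisons also do not depend on relatedness. SAP 9.2 tabulates all treatment-emergent, serious, Grade 3 or higher and discontinuation-related events, events of special interest, and deaths by arm. Thromboembolic and bleeding events are reported within 24 hours whether or not serious and whatever their cause (Protocol 9.1.2), and the SAP finds them by standardised MedDRA query. Serious events within the reporting window are reported regardless of causality (Protocol 9.4), and Protocol 9.1.3 still requires clinically significant bleeding to be reported as an event of special interest.

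All of this stands and limits the harm. It does not close the gap. Blinding does not make the related-event counts consistent, and the safeguards do not cover late serious events or the non-bleeding efficacy-endpoint events whose reporting depends on the causality answer.

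**Conclusion.** The point holds as a defect in a stated rule. The two definitions do not cover all events, and the strict Yes condition contradicts the sentence that follows it. The uncovered event, with compatible timing and another identifiable cause, is likely to be common because every subject has cancer and is on chemotherapy. That likelihood is a judgement from eligibility and dosing schedule, since no frequency is given.

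Classification will vary between investigators across about 75 planned sites, and related events will be under-counted wherever the Yes condition is applied literally. The effect is confined to the four uses of relatedness listed above. For suspected unexpected serious reactions it also depends on how far the sponsor relies on the investigator's answer, which the protocol leaves to local requirements and sponsor policy. The correction is worth making, but the trial's overall safety comparison does not rest on it.

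**What to change.** Replace the two bullets in Protocol 9.1.1 with definitions that are exhaustive and mutually exclusive, using the standard the protocol already states:

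- **Related**: there is a reasonable possibility, supported by facts or arguments, that IP caused or contributed to the event, whether or not other causes are present.
- **Not related**: there is no such reasonable possibility.

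Keep the listed factors as guidance and bring the eCRF completion guide into line.

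The drafting is two sentences, but the change is a protocol amendment and needs ethics review under Protocol 12.3. More events will be classed as related. SAP 8.7 says the monitoring board has been convened and SAP 9.4.6 describes an eCRF update in April 2020, so the study may already be under way. If so, record the effective date, so that events judged under the present definitions can be identified, or re-assessed while investigators are still blinded.
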